3.5 Estimated Study Duration

3.5.1 Study Duration for Subjects

The estimated study duration for each subject is approximately 7 months. This includes a 35-day screening period prior to the first dose of investigational product and an on-study period of approximately 169 days. If there is a clinically significant clinical or laboratory abnormality in need of monitoring, subjects will be followed until resolution of the abnormality or until the subject is considered clinically stable in the opinion of the principal investigator.

3.5.2 End of Study

Primary Completion: The primary completion date is defined as the date when the last subject is assessed or receives an intervention for the final collection of data for the primary endpoint(s), for the purposes of conducting the primary analysis, whether the study concluded as planned in the protocol or was terminated early.

If the study concludes prior to the primary completion date originally planned in the protocol (ie, early termination of the study), then the primary completion will be the date when the last subject is assessed or receives an intervention for evaluation in the study (ie, last subject last visit).

End of Study: The end of study date is defined as the date when the last subject is assessed or receives an intervention for evaluation in the study (ie, last subject last visit), following any additional parts in the study (eg, long-term follow-up), as applicable.

4. SUBJECT ELIGIBILITY

4.1 Inclusion Criteria

- 101. Subject's legally acceptable representative has provided informed consent and the subject has provided written assent based on local regulations and/or guidelines prior to initiation of any study-specific activities/procedures
- 102. Ambulatory male or female children 5 to less than 12 years of age (cohorts 2, 4, and 6) or adolescents 12 to less than 18 years of age (cohorts 1, 3 and 5) upon entry into screening
- 103. Clinical diagnosis of OI defined as a clinical history consistent with type I-IV OI as determined by presence of expected phenotype (eg, facial shape, voice, blue sclera, dentinogenesis imperfecta, typical radiographic features, fracture pattern) and lack of additional features unrelated to type I-IV OI (eg, blindness, mental retardation, neuropathy, craniosynostosis, premature exfoliation of deciduous teeth)
 - If familial, also must be autosomal dominant

4.2 Exclusion Criteria

- 201. History of an electrophoresis pattern inconsistent with type I to type IV OI
- 202. History of known mutation in a gene other than type I collagen alpha 1/type I collagen alpha 2 (COL1AI/COL1A2) causing OI or other metabolic bone disease
- 203. History of congenital dislocation of the radial head, interosseous membrane calcification, or exuberant callus formation
- 204. History of osteomalacia or rickets
- 205. Body weight less than 10 kg or greater than 90 kg
- 206. History of other bone diseases that affect bone metabolism (eg, osteoporosis pseudoglioma syndrome, idiopathic juvenile osteoporosis, osteopetrosis, hypophosphatasia)
- 207. History of Kawasaki disease, rheumatic myocarditis, ischemic cardiomyopathy, inherited cardiomyopathies, nephrotic syndrome, familial hypercholesterolemia, stroke, or any thromboembolic disorder
- 208. Evidence of untreated or unhealed oral cavities or oral infections
- 209. Unhealed or planned invasive dental or tooth procedure; removal of baby teeth is acceptable and not considered an invasive dental procedure
- 210. Unhealed fracture as defined by orthopedic opinion
- 211. Osteotomy, rodding surgery or spinal fusion surgery within 5 months prior to screening, or not yet healed per orthopedic surgeon

- 212. Any planned major surgery, including skeletal surgery (eg, rodding surgery, spinal surgery) within the next 6 months from day 1 that would interfere with study procedures or would require missing of any IP
- 213. Symptoms associated with skull abnormalities such as basilar invagination, basilar impression or Chiari malformation (headache induced by coughing or straining for stool, or parasthesia or weakness)
- 214. History of malabsorption (in children with serum albumin < lower limit normal [LLN], malabsorption should be clinically ruled out by the investigator to confirm eligibility)
- 215. History of long QT syndrome
- 216. History of malignancy
- 217. History of any solid organ or bone marrow transplant
- 218. Positive blood screen for hepatitis B surface antigen (HbsAg), hepatitis B core antibody (HBcAb), or hepatitis C antibody (HepCAb), human immunodeficiency virus (HIV) -1 or -2 antibody
- 219. History of hyper- or hypothyroidism, unless subject is on stable therapy
 > 6 months and has supporting laboratory documentation within 6 months prior to or at screening indicating normal serum thyroid-stimulating hormone [TSH] value
- 220. Evidence of any of the following:
- Current hyper- or hypoparathyroidism (parathyroid hormone outside the normal range)
 - Renal disease: Estimated glomerular filtration rate (eGFR)
 < 60 mL/min/1.73 m² (calculated by the bedside Schwartz equation at screening)

 $eGFR (mL/min/1.73 m^2) = 0.413 X (height/serum creatinine)$

- 1. (Height is in centimeters, and serum creatinine is in mg/dL)
- Current hypocalcemia (albumin-adjusted serum calcium < LLN of the laboratory's reference range) or hypercalcemia (albumin-adjusted serum calcium > ULN of the laboratory's reference range) at the time of screening. Serum calcium levels may be retested once in case of an elevated serum calcium level within 1.1 x ULN of the laboratory's reference range.
- Serum phosphorous < LLN
- Vitamin D insufficiency, defined as 25OHD levels < 20 ng/mL; vitamin D repletion will be allowed and subjects may be retested.
- Aspartate aminotransferase (AST), alanine aminotransferase (ALT)
 > 1.5 x upper limit of normal (ULN)
- Total bilirubin > 1.5 x ULN (subjects with Gilbert syndrome are eligible)
- 221. Prior treatment with:
 - romosozumab or other anti-sclerostin antibody

- fluoride or strontium for bone disease
- parathyroid hormone (PTH) or PTH derivatives within 12 months prior to screening
- Denosumab within 12 months prior to first dose of romosozumab
- zoledronic acid within 6 months prior to first dose of romosozumab
- oral bisphosphonates or intravenous bisphosphonates other than zoledronic acid if the first dose of romosozumab would be before their next scheduled bisphosphonate dose would have been given
- 222. Subject unwilling to stop IV or oral bisphosphonate prior to the first dose of IP
- 223. Administration of any of the following treatment within 3 months prior to screening:
 - Systemic glucocorticoids (≥ 5.0 mg prednisone equivalent/day for more than 10 days) within 3 months prior to screening. Topical and inhaled glucocorticoids will be allowed
 - Growth hormone (subjects on stable dose of growth hormone for at least 3 months prior to screening will be allowed)
 - Calcitonin
 - Other bone active drugs including anticonvulsants (except gabapentin and benzodiazepines) and heparin
 - Chronic systemic ketoconazole, androgens (except subjects who have received testosterone therapy for physiologic replacement in the setting of documented hormonal deficiency), adrenocorticotropic hormone (ACTH), cinacalcet, aluminum, lithium, protease inhibitors, gonadotropin-releasing hormone agonists
- 224. Currently receiving treatment in another investigational drug study, or less than 30 days or 5x the half-life, whichever is longer, since ending treatment on another investigational drug study(s), or current or planned participation in a clinical trial that would preclude compliance with study requirements
- 225. Known intolerance to calcium or vitamin D supplements
- 226. History or evidence of any other clinically significant disorder, condition or disease that, in the opinion of the investigator or Amgen physician, if consulted, would pose a risk to subject's safety or interfere with the study evaluation, procedures or completion
- 227. History of alcohol or drug abuse
- 228. Unwilling or unable to abstain from nicotine or tobacco containing products or drug substances of abuse throughout the screening period and for the duration of the study

- 229. Females of reproductive potential who are unwilling to practice an acceptable method(s) of highly effective birth control while on study through day 169 (for subjects who remain on study through completion) or for 3 months after last dose of IP(for subjects who withdraw prior to end of study). Acceptable methods of highly effective birth control are described in Section 6.9.
- 230. Females with a positive pregnancy test, or who are currently pregnant or planning to become pregnant or who are lactating/breastfeeding while on study through day 169 (for subjects who remain on study through completion) or for 3 months after last dose of IP (for subjects who withdraw prior to end of study)
- 231. Subject will not be available for protocol-required study visits
- 232. Subject's parent or legal representative that, in the opinion of the investigator, may present with compromised ability to give written permission for informed consent
- 233. Less than 2 evaluable vertebrae by DXA evaluation in the region of interest, L1-L4, as confirmed by the central imaging laboratory.
- 234. Subject has known sensitivity to any of the products or components to be administered during dosing
- 235. Subject previously has enrolled in this study
- 236. Clinically significant valvular heart disease based on local echocardiogram (ECHO) results.

5. SUBJECT ENROLLMENT

Before subjects begin participation in any study-specific activities/procedures, Amgen requires a copy of the site's written institutional review board/independent ethics committee (IRB/IEC) approval of the protocol, informed consent form (ICF), assent, and all other subject information and/or recruitment material, if applicable (see Section 11.2). All subjects and/or legally acceptable representatives must personally sign and date the ICF and subject should sign the subject assent form as applicable by local law before commencement of study-specific activities/procedures.

Subjects who reach 18 years of age (or legal age in the country indicated) during the study will need to provide informed consent by personally signing and dating the ICF.

Adverse events are to be collected for a subject once they are enrolled in the study. A subject is considered enrolled when the investigator confirms that the subject has met all eligibility criteria (both screening and day 1 pre-dose assessments). The investigator is to document this decision and date in the subject's medical record and in/on the enrollment case report form (eCRF).

Each subject who enters into the screening period for the study (defined as when the informed consent and subject assent forms are duly signed) receives a unique subject identification number before any study-related activities/procedures are performed.

The subject identification number will be assigned using interactive response technology (IRT). This number will be used to identify the subject.

The subject identification number must remain constant throughout the entire clinical study; it must not be changed after initial assignment, including if a subject is rescreened.

The subject identification number will be 11 digits: the first 3 digits are the protocol identifier (227), the next 5 digits consist of the 2-digit country code (66, US) and the 3-digit study-specific site number (001), and the last 3 digits are assigned in incremental order within each site as subjects are screened starting at 301. Thus, the identification for the first subject screened at site 001 in the US will be **Exercise**, the identification number for the second subject screened at site 001 will be **Exercise**, and so forth.

6. TREATMENT PROCEDURES

6.1 Classification of Product

The Amgen investigational products used in this study is romosozumab

The other protocol-required products used in this study include: calcium and vitamin D.

The Investigational Product Instruction Manual (IPIM), a document external to this protocol, contains detailed information regarding the storage, preparation, destruction, and administration of romosozumab.

6.2 Investigational Product

All investigational product (IP) romosozumab will be administered at the research facility by a qualified staff member.

A physician must be available at the time of administration of Investigational Product.

6.2.1 Amgen Investigational Product – Romosozumab

Romosozumab for SC will be manufactured and packaged by Amgen Inc. and distributed using Amgen clinical study drug distribution procedures. Romosozumab will be provided in a 3 cc sterile vial filled with 1 mL deliverable volume of 90 mg/mL romosozumab. The SC doses for this study are capped at 1.5 mL per injection. Doses split into multiple syringes will be injected into separate sites. New injections will be given at least 1 inch from an old site.

6.2.1.1 Dosage, Administration, and Schedule

Amgen will supply romosozumab to study sites.

Subjects will receive romosozumab via SC injection on days **and the second second**, according to the Schedule of Assessments (Table 6). At the end of the initial **and the second second**

subject's weight assessed at the time of dosing.

The date and time of IP administration will be recorded on the eCRF.

The planned dose levels and cohorts are described in the table below.

Cohort #	Age Group (years of age)	Dose ^a	Dosing Day	N	
1	12 to less than 18		-	4	
2	5 to less than 12			4	
3	12 to less than 18			4	
4	5 to less than 12			4	
5 (optional)	12 to less than 18			4	
6 (optional)	5 to less than 12			4	

 Table 2. Planned Dose Cohorts

^a All doses will be administered subcutaneously

6.2.1.2 Dose-cohort Study Escalation and Stopping Rules

The planned doses of romosozumab are shown in Table 2. IP will be administered on day, day and day following all required pre-dose procedures.

The dosing schedule is described by a schema in the protocol synopsis.

6.2.1.2.1 Dose Level Review Meetings

A dose level review meeting (DLRM) will be held to review data and monitor safety before escalation to the next higher dose or expansion to the younger age cohort. The DLRT members will be composed of, at a minimum, the investigators actively enrolling subjects at the time of the meeting (ie, have subjects in screening or already enrolled), the Amgen Medical Monitor, and Amgen Global Safety Officer or designated safety scientist, Amgen Clinical Research Study Manager or designee, and biostatistics representative or designee. Additional members may be added as needed (eg, PK scientist). The DLRT voting members include the principal investigator or designee, Amgen Medical Monitor and Amgen Global Safety Officer or designee.

The DLRT voting members are responsible for dosing recommendations, which may include escalation to the next planned dose, escalation to an intermediate dose (a dose lower than the next planned dose), de-escalation to a lower dose; continuation, delay, or termination of dosing; or repetition or expansion of a cohort. Clear stopping rules will be followed, and ad hoc DLRMs will be held if necessary. All available study data, including demographics, medical history, concomitant medications, adverse events, electrocardiograms (if applicable), vital signs, and clinical laboratory test results will be reviewed.

The Amgen Medical Monitor will review data on an ongoing basis throughout the duration of study.

Investigators who are not actively enrolling subjects at the time of the DLRM will not participate in the DLRM. They will be informed of the recommendations of the DLRM.

6.2.1.2.2 Dose Stopping Rules

Determination of the severity of adverse events will be based on the **Severity Intensity** Scale **for Adverse Events**.

The DLRT will recommend stopping or modifying dosing if suspected adverse drug reactions, changes in vital signs, electrocardiogram (ECG), or clinical laboratory results are observed and these changes pose a significant health risk. In addition, dosing will be stopped or modified if any of the stopping rules shown in Table 3 are met. The Amgen Medical Monitor will review data in an ongoing basis, may suspend dosing and convene a DLRM at any time based on emerging safety data.

Clinically or medically significant suspected adverse drug reactions, and serious adverse events considered to be related to study procedures will be followed until resolved or considered stable.

The study may be terminated at any point at the discretion of the sponsor.

Scenario	Action			
Any occurrence of a Severity Intensity Scale	 Stop dosing additional subjects and convene DLRM (if event occurs outside of the regularly scheduled DLRM) 			
for Adverse Events moderate suspected adverse drug reaction of the same system organ class (eg, hepatobiliary, cardiovascular) in 2 or more subjects in the same cohort	 Review adverse event and all relevant safety data for evidence of relationship to treatment and clinical or medical significance Based on the DLRM vote, one of the following decisions may be made: stop enrollment of the cohort (if applicable) resume enrollment of the cohort as planned continue enrollment of the cohort at a lower dose expand the cohort at the same dose continue enrollment of the study at a lower dose upon unanimous vote escalate to an intermediate dose (a dose lower than the next planned dose) upon a unanimous vote escalate to the next planned dose 			
Any occurrence of a Severity Intensity Scale for Adverse Events severe suspected adverse drug reaction	 Stop dosing additional subjects and convene DLRM (if event occurs outside of the regularly scheduled DLRM) Review adverse event and all relevant safety data for evidence of relationship to treatment and clinical or medical significance If the adverse event is determined by a majority vote of the DLRT to be related to study drug and clinically or medically significant, recommend that no further doses should be administered at this dose and no dose escalation should proceed. Recommend that enrollment of the study continue at a lower dose or a lower dose cohort may be added to the study. Otherwise based on majority vote of the DLRT, one of the following decisions may be made: resume enrollment of the cohort as planned continue enrollment of the study at a lower dose or add a lower dose cohort to the study 			

Table 3.	Cohort	Dose	Stopping	Rules
----------	--------	------	----------	-------

DLRM = dose level review meeting; DLRT = dose level review team

6.2.1.3 Dosage Adjustments, Delays, Rules for Withholding or Restarting, Permanent Discontinuation

Romosozumab will be administered as a weight-based dose determined based on each subject's weight assessed at the time of dosing. Romosozumab will be administered at a dose of mg/kg, mg/kg or up to mg/kg body weight.

If a subject misses a scheduled dose of IP during a study visit, then he/she should return to the clinic to receive the missed dose within the visit window allowed for that particular visit (see Section 7.2). The clinical monitor should be contacted for specific instructions if a subject cannot receive his/her dose within the allowed visit window.

If a subject discontinues IP early, the investigator is to discuss with the subject the appropriate processes for discontinuation and the option to continue study assessments until day 169. The investigator must document the change to the Schedule of Assessments and the level of follow-up that is agreed to by the subject (eg, in person, by telephone/mail, through family/friends, in correspondence/communication with other physicians, from review of the medical records).

Serum calcium and phosphorus concentrations will be closely monitored during the study.

6.3 Other Protocol-required Therapies

All other protocol-required supplements, including calcium and vitamin D, that are commercially available are not provided or reimbursed by Amgen (except if required by local regulation). The investigator will be responsible for obtaining supplies of these drugs.

All subjects are required to take daily supplements of 30-50 mg/kg (not to exceed 1000 mg calcium) and at least 800 IU vitamin D for the duration of the study to minimize the risk of hypocalcemia.

If a subject becomes hypercalcemic over the course of the study, the calcium and/or vitamin D supplementation may be discontinued until serum calcium concentrations has returned to the normal range.

If a subject becomes hypocalcemic over the course of the study, the calcium and/or vitamin D supplementation may be increased, per medical judgment of the investigator.

In instances where a subject is experiencing tolerability issues with daily elemental calcium, the subject should be instructed to try different calcium salt formulations. If this strategy fails, the investigator may document that only a lower calcium supplementation dose is tolerated by the subject or that dietary supplementation is required and this will be allowed. Tolerability issues for vitamin D should be managed using the same approach as outlined for calcium above.

The dose, start date, stop date, and frequency for calcium and vitamin D are to be recorded on the eCRF. The reason for dose change of calcium and/or vitamin D supplementation is to be recorded on the eCRF.

6.4 Hepatotoxicity Stopping and Rechallenge Rules

Subjects with abnormal hepatic laboratory values (ie, alkaline phosphatase [ALP], AST, ALT, total bilirubin) and/or international normalized ratio (INR) and/or signs/symptoms of hepatitis (as described below) may meet the criteria for withholding or permanent discontinuation of Amgen IP or other protocol-required therapies as specified in the Guidance for Industry Drug-induced Liver Injury: Premarketing Clinical Evaluation, July 2009.

6.4.1 Criteria for Permanent Withholding of Amgen Investigational Product and Other Protocol-required Therapies due to Potential Hepatotoxicity

Investigational product and other protocol-required therapies, as appropriate, should be discontinued permanently and the subject should be followed according to the recommendation in Appendix A (Additional Safety Assessment Information) for possible drug-induced liver injury (DILI), if all the criteria below are met:

- Total bilirubin > 2x upper limit of normal (ULN) or INR > 1.5
- AND increased AST or ALT from the relevant baseline value as specified below:

Baseline AST or ALT value	AST or ALT elevation				
< ULN	> 3x ULN				

- AND no other cause for the combination of the above laboratory abnormalities is immediately apparent; important alternative causes for elevated AST/ALT and/or total bilirubin values include, but are not limited to:
 - Hepatobiliary tract disease
 - Infectious hepatitis (eg, hepatitis A/B/C/D/E, Epstein-Barr Virus, cytomegalovirus, herpes simplex virus, varicella, toxoplasmosis, and parvovirus)
 - Right sided heart failure, hypotension or any cause of hypoxia to the liver causing ischemia.
 - Exposure to hepatotoxic agents/drugs or hepatotoxins, including herbal and dietary supplements, plants and mushrooms
 - Heritable disorders causing impaired glucuronidation (eg, Gilbert's Syndrome, Crigler-Najjar syndrome) and drugs that inhibit bilirubin glucuronidation (eg, indinavir, atazanavir)
 - Alpha-one antitrypsin deficiency
 - Alcoholic hepatitis
 - Autoimmune hepatitis
 - Wilson's disease and hemochromatosis
 - Nonalcoholic fatty liver disease including steatohepatitis (NASH)
 - o Non-hepatic causes (eg, rhabdomylosis, hemolysis)

6.4.2 Criteria for Conditional Withholding of Amgen Investigational Product and Other Protocol-required Therapies due to Potential Hepatotoxicity

The following rules are recommended for withholding of IP and other protocol-required therapies:

• Elevation of either AST or ALT according to the following schedule:

Baseline AST or ALT	AST or ALT Elevation
value	AST OF ALT Elevation
Any	> 8x ULN at any time
Any	$>$ 5x ULN but $<$ 8x ULN for \ge 2 weeks
Any	> 5x ULN but < 8x ULN and unable to adhere to protocol enhanced monitoring schedule
Any	> 3x ULN with clinical signs or symptoms that are consistent with hepatitis (such as right upper quadrant pain/tenderness, fever, nausea, vomiting, and jaundice).

- OR: TBIL > 3x ULN at any time
- OR: ALP > 8x ULN at any time

Investigational product and other protocol-required therapies, as appropriate, should be withheld pending investigation into alternative causes of DILI. If IP is withheld, the subject is to be followed according to recommendation in Appendix A for possible DILI. Rechallenge may be considered if an alternative cause for impaired liver tests (ALT, AST, ALP) and/or elevated total bilirubin is discovered and the laboratory abnormalities resolve to normal or baseline.

6.4.3 Criteria for Rechallenge of Amgen Investigational Product and Other Protocol-required Therapies After Potential Hepatotoxicity

The decision to rechallenge the subject should be discussed and agreed upon unanimously by the subject, the subject's legally acceptable representative, investigator, and Amgen.

If signs or symptoms recur with rechallenge, then IP and other protocol-required therapies, as appropriate should be permanently discontinued. Subjects who clearly meet the criteria for permanent discontinuation (as described in Section 6.4.1) should never be rechallenged.

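### The permanent-discontinuation rule for liver injury (Protocol 6.4.1) has no AST/ALT criterion for baselines from ULN to 1.5x ULN, which exclusion 220 admits

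*Protocol*

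**What the plan says.** **Protocol 6.4.1.** Investigational product, and other protocol-required therapies as appropriate, "should be discontinued permanently and the subject should be followed according to the recommendation in Appendix A" if three criteria all hold:

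1. total bilirubin > 2x ULN or INR > 1.5;
2. "AND increased AST or ALT from the relevant baseline value as specified below", followed by a table with one row: baseline < ULN, elevation > 3x ULN;
3. no obvious alternative explanation.

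**Protocol 4.2, exclusion 220.** A child is excluded if AST or ALT is "> 1.5 x upper limit of normal (ULN").

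**Protocol 6.4.2.** "The following rules are recommended for withholding of IP and other protocol-required therapies". Every AST/ALT row here applies to any baseline: > 8x ULN; > 5x to < 8x ULN lasting 2 weeks or more; "> 5x ULN but < 8x ULN and unable to adhere to protocol enhanced monitoring schedule"; > 3x ULN with clinical features of hepatitis. Two further lines follow: "OR: TBIL > 3x ULN at any time" and "OR: ALP > 8x ULN at any time".

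**Protocol 6.4.3.** A child who clearly meets 6.4.1 may never be rechallenged. Any other rechallenge needs unanimous agreement of subject, representative, investigator and sponsor.

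**Protocol Appendix A.** Concurrent enzyme and bilirubin/INR elevation must be reported as a serious adverse event within 24 hours, with the criteria defined by reference to Section 6.4. Separately, close observation applies to AST or ALT > 3x ULN, or to a 2-fold rise in children whose values were raised before drug.

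**The concern.** The rule asks for a rise from the relevant baseline, but then names only one baseline category, and eligibility is wider than that category. Two eligible children with identical on-study liver values can therefore get different answers from the protocol's own hepatic rule, solely because of a baseline that the protocol permits.

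Three consequences hang on 6.4.1 for the child with the raised baseline: permanent discontinuation is not called for, the absolute rechallenge ban does not attach, and the automatic 24-hour report in Appendix A is unclear because it points back to Section 6.4. While doses remain, stopping and rechallenge are at stake. After the last dose, what remains is the automatic report and whether calcium and vitamin D should be stopped. No endpoint, estimate or sample size is affected.

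**Working it through.** The plan gives no figure to reproduce. The check applies the stated rules in order to one set of values, in multiples of ULN.

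**Inputs.** Baseline ALT *b*; on study ALT 4x, bilirubin 2.5x, ALP 1.5x, INR 1.0; no symptoms; no other apparent cause. These are illustrative values, not rates. AST is assumed not to qualify separately: a child whose AST was normal at baseline and then exceeded 3x ULN could meet 6.4.1 on that enzyme.

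**Step 1: eligibility.** Exclusion 220 applies only if *b* > 1.5. Baselines of 0.8, 1.0, 1.2 and 1.5 are all admitted.

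**Step 2: 6.4.1.** The bilirubin criterion holds (2.5 > 2), as does the criterion on other causes. The AST/ALT criterion needs *b* < 1 and ALT > 3.

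| Baseline ALT | Has a row? | 6.4.1 met? |
|---|---|---|
| 0.8x | yes | yes |
| 1.0x | no | no |
| 1.2x | no | no |
| 1.5x | no | no |

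**Step 3: 6.4.2, any baseline.**

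| Line | Value | Met? |
|---|---|---|
| AST/ALT > 8x | 4x | no |
| > 5x to < 8x, sustained or monitoring not followed | 4x | no |
| > 3x with features of hepatitis | asymptomatic | no |
| Bilirubin > 3x | 2.5x | no |
| ALP > 8x | 1.5x | no |

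So at baselines of 1.0x, 1.2x and 1.5x no rule in Section 6.4 is met.

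**Step 4: extent of the gap.** For an asymptomatic child whose relevant enzyme started at ULN to 1.5x ULN, with no other apparent cause and ALP at or below 8x ULN, the gap is:

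- AST/ALT > 3x to 5x ULN, or > 5x to < 8x ULN for under 2 weeks with monitoring followed; together with
- bilirubin > 2x to 3x ULN, or INR > 1.5 with bilirubin at or below 3x ULN.

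Features of hepatitis, including jaundice, close the gap through 6.4.2. The INR limb will arise mostly in children already under close observation, because INR is not in the scheduled chemistry panel (Protocol 7.4.13.1).

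**Step 5: when it can matter.** SAP Appendix A lists 7 post-baseline chemistry visits: days 8, 29, 57, 64, 85, 113 and 169. With screening and day 1 that is 7 + 2 = 9, which agrees with Protocol Table 9. Follow-up starts at day 64, so at most 3 scheduled visits (days 8, 29, 57) fall where stopping could still matter. The dosing days are blacked out, so 3 is an upper bound. The reporting question can arise at all 7.

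**Step 6: a threshold of > 3x ULN for any baseline.** The example then meets 6.4.1 at every admitted baseline. The implied fold rise is more than 3/1.0 = 3.0 at baseline ULN and more than 3/1.5 = 2.0 at baseline 1.5x ULN, so never below the 2-fold measure in Appendix A. A threshold of 3x baseline would be 3 × 1.0 = 3.0x to 3 × 1.5 = 4.5x ULN. It would still miss ALT 4x at baseline 1.5x.

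**The case against.** **The table may be incomplete in the copy read.** The point rests on an absent row, and tables here were machine-read. A row for raised baselines may have been lost, or the cell may have read at or below ULN, which would cover a baseline exactly at ULN but nothing above it. The row reads intact and the text after it continues normally, so a loss is possible but not shown. This stands as a reason to check the source first.

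**The child is not unprotected.** This largely stands, and it sets the severity.

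- Close observation applies above 3x ULN at any baseline, with retesting every 24 hours if bilirubin is > 2x ULN or INR > 1.5.
- Under Protocol 6.2.1.2.2 the dose level review team will recommend stopping or modifying dosing for laboratory changes that pose a significant health risk, and the Medical Monitor may suspend dosing.
- Protocol 8.3.1 allows removal for a safety concern.
- Appendix A keeps a serious-event route for other potential drug-induced liver injury that meets the general criteria, and Protocol 9.1.2 names such injury as an example.

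These limit the harm. They do not explain why the explicit rule answers differently for identical values.

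**The rules are advisory and cite outside guidance.** 6.4.1 says should, 6.4.2 is a recommendation, and Section 6.4 speaks of criteria "as specified in the Guidance for Industry Drug-induced Liver Injury: Premarketing Clinical Evaluation, July 2009". That is fair: this is an incoherent rule, not a missing mandatory stop. These documents give no threshold from that guidance, so it cannot be used to fill the missing row.

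**A stronger reading through the SAP.** SAP 9.6.6 defines Hy's law (AST or ALT > 3x, bilirubin > 2x, ALP < 2x ULN within 7 days) with no baseline condition, so the example is a Hy's law case that met no Section 6.4 rule. A reader might infer that the missing row causes a conflict between protocol and SAP, and that adding it removes the conflict. The documents do not support that. The two definitions differ by design: 6.4.1 has INR and alternative-cause limbs, and the SAP has an ALP limb. An asymptomatic child with a normal baseline, the example's on-study values and an apparent viral cause also meets neither 6.4.1 nor 6.4.2, before or after the change.

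**Conclusion.** The gap is real on the text as it reads, and it is minor. For an enzyme starting at ULN to 1.5x ULN, 6.4.1 has no AST/ALT criterion and 6.4.2 does not cover the range in Step 4. From a normal baseline, the same values call for permanent discontinuation and bar rechallenge.

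This rests on the source table having no further row, on an asymptomatic child with no other apparent cause, and on the second enzyme not qualifying by itself.

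The size can be stated only at the level of the rule. The documents give neither the distribution of baseline enzymes nor the rate of such events, so no number of affected children follows. A reader might also infer that a child with liver injury would go on being dosed without oversight. The backstops above rule that out. What is lost is the explicit stop, the absolute rechallenge ban and the clarity of the automatic report.

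**What to change.** First check the source table in Protocol 6.4.1 for a further row; if there is one covering these baselines, the point closes. If not, at the next amendment change the baseline cell from < ULN to Any, the term 6.4.2 already uses, and keep > 3x ULN. This matches the close-observation threshold in Appendix A and the AST/ALT threshold in SAP 9.6.6. The rechallenge ban in 6.4.3 and the reporting trigger in Appendix A then follow without further edits.

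The cost is one table cell, with no new sample, visit or procedure. The downside is that a child with a raised baseline may be stopped slightly sooner. The change will not make 6.4.1 identical to the SAP's Hy's law definition, and it need not.
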